Additional sites will be selected from those participating in the GPFH Mental Health In-Patient pilot study (GPMH) and similar methodology employed. Comparisons for both TP and GPMH will be required with reference GP fundholding practices. For TP sites with a special interest in mental health and GPMH sites, reference GP fundholders will be identified which use the same major provider of mental health services as the TP and GPMH sites, and which are so far as possible matched for rurality and social class mix of the practice populations. Details and justification for the types of comparison that can be made between different purchasing models are included as a separate paper which is attached as an Appendix to this proposal.

Some of the important information on reference GP fundholding practices may be able to be collected retrospectively from routine sources or as part of the initial data collection, especially where it relates to the purchasing plans of health commissions, or to configuration of secondary care services.

For the study of outcomes related to patients, methodology combining both limited quantitative data collection directly from patients and qualitative data collection from patients and other stakeholders within the community representing service users will be employed within the special study sites.

STUDY 1: STRATEGIC APPROACHES AND SERVICES PROVIDED FOR MENTAL HEALTH

This section of the study will address the following groups of questions, comparing Total Purchasing sites (with and without a special interest in mental health), GPFH practices, and reference GP fundholders initially and at follow-up:

* Accessibility: are the services available to and planned for severely mentally ill people and to the professional staff caring for them different with respect to their range, including the Care Programme Approach, and what is relative role of TP and GPMH sites in influencing changes in service provision?

- * Utilisation: are there differences in the use of mental health services (referral and admission) between TP sites, GPMH sites and reference practices?
- * Need assessment and information: are there differences in the approach to need assessment and differences in relevant information systems within the district and the providers?
- * Relationships with Authorities: do the structural relationships with DHAs, FHSAs and Local Authorities (including housing agencies) differ?

Methods

Identifying sites, and aims of individual sites

Total purchasing sites with a special interest in mental health problems are being identified during an initial series of visits to all sites which are due to be complete by the end of 1996. GPMH sites have, by definition an interest in mental health problems. By a combination of telephone interview and site visits, standard fundholding practices will be identified which can act as reference practices for the TP and GPMH sites. The aims of individual sites will be established by a combination of information from their purchasing plans, and interviews with lead GPs and fund managers.

Accessibility of services

Information about availability of services will be obtained partly at the initial interview at every Total Purchasing site. Sufficient information will be needed at this interview to characterise current service provision for sites with a mental health interest to identify reference practices. This basic information on availability of services will need to be supplemented during telephone interviews in early 1996. Subsequent data on availability will be collected by questionnaire or

telephone interview focused on mental health problems with the Total Purchasing manager at every site in late 1996 or early 1997. Information will also be collected from key stakeholders and providers in GPMH sites in the first part of 1996, and subsequently, depending on when they have 'live' budgets.

The composite information collected from questionnaires and telephone interviews will cover details of provider contracts (which may tend to focus on more severely mentally ill people) and of services bought in to the site (which may tend to focus on more minor mental illnesses) and also the site's strategic aims and intentions for developments, including the Care Programme Approach. (The functioning of the CPA may be able to be assessed by asking sites specifically to collect data on the number of CPA meetings attended by GPs, this information being sought from practices or provider groups.) This part of the study will address all mental health services, not just those related to severely mentally ill people.

Information on availability of services will be collected from all Total Purchasing sites, allowing comparison between Total Purchasing sites with and without a special interest in mental health (see appendix). Contracts will be reviewed to assess what are the aims for the quality and provision of services, and also the criteria for assessing quality.

A different perspective on the availability of services will also be sought from all the Provider units related to a sample of the Total Purchasing sites with and without a special interest in mental health and from GPMH sites. By means of telephone interviews with Clinical Directors followed where necessary by personal visits, the relative contributions of the different purchasing models to changes in the availability and configuration of services will be defined, comparing the start-up period with one year later.

Utilisation of services

Information about *utilisation* of services will be obtained from hospital in-patient episode databases, focusing on admission rates and length of stay for patients with diagnoses in ICD9 Chapter V who are registered with GPs in each Total Purchasing site, in GPMH practices, and also in each reference site. These data will be analysed for April 1995 to March 1996, and for April 1996 to March 1997. Information will be sought from the study sites about any action taken to reduce admissions and length of stay, e.g. the employment of nurses to visit the in-patient units to expedite discharge.

For out-patient referrals information will be sought from the relevant providers including practices and Community Mental Health Teams by means of available databases (including practice billing systems) and also through individual Community Psychiatric Nurse workload schedules in the sample of Total Purchasing, GPMH and reference sites selected for special study. This will depend on the availability of routine nursing data being available from existing sources. Reliable

outpatient information will be difficult to collect because of the wide variety of types of secondary mental health contact, and it will not be possible to determine how much out patient data will be collected until individual sites are visited. Changes in outpatient utilisation rates are not essential to this part of the study.

Needs assessment and information systems

Information about need assessment and information systems including the use of registers will be sought by telephone interview or questionnaires to the relevant managers of each Total Purchasing, GPMH and reference site included in the sample for special study. This will be supplemented by telephone interviews both with the relevant managers of the providers used by the special study sites and also with representatives of the relevant Health Authorities or Commissions (the first contact being aimed at a Consultant in Public Health Medicine).

Relationships with Health Commissions and Local Authorities

Information about relationships with authorities will be obtained during the same telephone interviews of the relevant managers of each Total Purchasing, GPMH and reference site included in the sample for special study and with representatives of the relevant Health Authorities or Commissions (probably Consultants in Public Health Medicine). It will be supplemented by telephone interviews with representatives of the relevant Local Authorities and Housing Departments if information about those areas is not obtained via the Health Authorities.

The data collection exercise for Total Purchasing sites, GPMH sites and reference sites will be repeated after 12 months of operation of the schemes, allowing for identification of changes before and after the sites had budgets which included the full range of mental health services.

Sample size and power

In relation to strategic aims and configuration of services, data will be collected from all the TP and GPMH sites. For admission rates, data will be collected and analysed from routine data available at the National Casemix Office in Winchester. The sample size of both groups is fixed and any modest increase of statistical power from choosing more than one reference site for each TP or GPM site would add relatively little to the study. Power calculations were done on recent data from 2 East Anglian counties which had mean (geometrical mean) psychiatric admission rates of 0.8 and 0.4 admissions per 1000 patients per year. The study would have the power to detect a reduction in rates in TP sites to 0.55 and 0.3 respectively, i.e. a reduction in admission rate of between a quarter and a third (80% power, 5% significance). The power to detect changes in admission rates in GPMH sites will be less than this because of their reduced numbers.

Assessment instruments

Interview schedules will be drawn up as part of the overall approach to collection of information about the TP and GPMH sites, and related interview schedules will be used for visits and telephone interviews for follow-up, for the reference GP fundholders, and for the relevant Health and Local Authorities.

STUDY 2: THE IMPACT OF PURCHASING DECISIONS ON OUTCOMES FOR SEVERELY MENTALLY ILL PEOPLE

This section will address the following groups of questions relating to severely mentally ill people, looking at changes over time and differences between TP, GPMH and other GPF sites:

- * Are patient outcomes different as reported by patients and carers (including how many severely mentally ill people fall out of contact with the specialist services, and rate of unplanned admissions or readmissions)?
- * Do the accessibility and quality of services provided differ for patients between TP, GPMH and other GPF sites, and why?
- * Are there differences in the removal of severely mentally ill people from the practice lists?
- * Are there differences in the involvement of patients in the Care Programme Approach?

Methods

Methodology combining both limited quantitative data collection directly from patients and qualitative data collection from patients and other stakeholders within the community representing service users will be employed within the special study sites.

A sample of districts will be chosen which contain new study sites (either TP or GPMH). In each district qualitative methods will be employed to obtain views of key stakeholders representing service users (eg. National Schizophrenia Fellowship, MIND, Community Health Councils, advocacy and user groups, and other relevant local voluntary agencies) with respect to the questions of accessibility and quality given above, with specific regard to severe and enduring mental illness. These will identify the domains of quality regarded as important by the various groups, and explore the extent to which quality is judged to have improved as a result of changes which have actually taken place in the TP and GPMH practices. We will distinguish between views expressed as a result of knowledge of the management of individual patients, and views about care in general.

Some quantitative measures of patient outcome will be collected directly from a sample of patients but the extent of this is yet to be determined. The sample size required to inform a quantitative

comparison is beyond the scope and budget of this proposal but some data on direct service use are required to inform the economic analysis.

Assessment instruments

A trained and experienced senior researcher will use a semi-structured approach to addressing the relevant questions. The interview exercise will be repeated after 12 months, again giving the opportunity to examine longitudinal changes. A final decision has not yet been taken on whether these interviews will take place on a one to one basis or in groups.

STUDY 3: THE IMPACT OF PURCHASING DECISIONS ON THE WORK OF PRIMARY CARE TEAMS AND SPECIALIST MENTAL HEALTH WORKERS

This section will address the following question, based on the CPNs working in relation to the selected sample of TP, GPMH and reference sites, with follow-up at one year:

* Are the mental health nurses targeted more explicitly on the most severely mentally ill people?

Methods

CPN working with mentally ill people on the practice lists at the selected TP, GPMH and reference sites will be identified at visits to the practices. The staff will be interviewed at their practice site twice, during Spring and Summer 1996, and one year later.

As in Study 1, questions will address the balance of use of resources within practices including purchasing from providers and buying in staff to work in the practices. However, more detailed information will be collected from staff, and may include some detailed collection of workload data. It is important that this section of the study addresses all mental health problems, not just those related to severely mentally ill people, as different purchasing models may alter the balance of CPN care committed to serious and less serious forms of mental illness.

Sample size

The data collection and analysis for this study will be mainly descriptive. Since a deliberate decision has been made to study a small number of sites in greater depth, the power of this study to detect quantitative differences in workload will be limited.

Assessment instruments

Interview schedules will be prepared for the mental health nurses, relating to their work and to patients whom they see. These will be based on the work of [name] who also works with the National Centre in Manchester.

STUDY 4: IMPACT OF TOTAL PURCHASING ON SERVICE COSTS AND EFFICIENCY

This part of the study will be carried out in collaboration with the economists involved in the Total Purchasing Evaluation Consortium ([name], York; [name], LSE; [name], Bristol; [name], Southampton). The aims of the economic aspects of this study are:

- * to examine service cost implications of any differences in service use by TP, GPMH sites and their comparators;
- * to explore the link between costs and outcomes.

Data will be collected on the NHS resource use by TP sites, GPMH sites and their comparators. Only direct costs will be considered, i.e. those that fall within the NHS or Social Services. Indirect costs (i.e. those incurred by users and informal carers) are beyond the scope of this study, given the resources available. The study will compare study sites to controls and will compare the initial position regarding services for mental health and illness at all study sites with the situation after the first year of operation.

Methods

Physical resource use

Data on the physical quantities of resources will be as far as possible collected prospectively as part of Study 1. Inpatient data including admission rates, length of stay and destination on discharge will be collected from HES data. For outpatient referrals and other services information will be sought through a combination of the Community Mental Health Team and individual Community Psychiatric Nurse workload schedules. Until individual sites are visited it will not be clear to what extent such data can feasibly be collected.

The evaluation of Total Purchasing includes assessment of transaction costs. It is not proposed to replicate this for GPMH sites, since contracting just for inpatient mental health services is unlikely to represent a long term purchasing model.

Unit costs

For unit costs, there is a choice of obtaining estimates from the sites themselves or of using nationally available data. The PSSRU have already undertaken an extensive review of unit costs within Mental Health and it would seem appropriate to draw upon this resource (Netten A, Detten J. Unit Costs of Community Care, PSSRU, 1995; see attached Table). However, unravelling the impact of local practices on prices might show that more high cost resources also deliver more effective care than those employed in the field more generally. We expect to collect some data locally on the prices of individual contracts, though comparisons will be resticted to contract prices rather than trying to cost each individual item of resource.

Outcomes

Measuring outcome and determining to what extent any differences in outcome are directly attributable to differences in service costs is complex. Although the evaluation will not be a full cost-effectiveness analysis it will describe any differences in outcomes detected in Study 2 and compare these with any differences found in overall service costs.

FUNDING FOR THE GROUP OF FOUR LINKED STUDIES

Some of the basic information for the first study is supported by funding from other parts of the total purchasing project. However further data collection from GPMH sites and comparators and visits to provider units involving a senior researcher will be needed as well as secretarial support and researcher's time for analysis and writing up.

For the second study an experienced researcher will again be needed to collect the qualitative and quantitative data at the study sites.

For the third study visits to the selected sites will once more be needed, involving an experienced researcher.

A composite budget for the first three studies is therefore as follows:

Experienced research assistant, 1.0 wte, 2 years	£48.0K
Senior Researcher's time, 0.1 wte, 1 year	£6.7K
Secretarial support, 0.2 wte, 2 years	£5.6K
Overheads at 40%	£24.1K
Travel and subsistence	£8.0K
Stationery, telephones etc.	£4.0K
TOTAL	£96.4 K

The field work would begin in January 1996, related to the lead-in period for Total Purchasing, for visiting GPMH practices and establishing a baseline for Total Purchasing and reference sites. Visits to the providers on the one hand, and to stakeholder groups on the other, would be spread evenly over the 18 months after April 1996, giving a 12 month follow-up for the various sites which would be entered into the study in a staggered manner. Time for analysis would also be allowed within the on-going survey work. The final writing up would occupy the last 3 months of the 2 year study.

Identical methods would be used to study standard fundholding which was extending to include mental illness in-patient treatment. Therefore there would be economies of scale and the time frame would also be identical.

The present funding proposal is for two years. The power of the study to detect differences between the purchasing models will be considerably enhanced if funding becomes available for an additional year, as this will give more time for service reconfiguration to take place.

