separate proposal and contract (not included in this proposal). The scope for using routine NHS data to monitor changes in the seven services discussed above is summarised in Table 5.2, which suggests that the routine data, notably the Hospital Episode Statistics (HES) in England, would provide valuable information in relation to three services: emergency admissions, maternity and regional specialties. HES can provide up-to-date data on all inpatient and day case episodes, along with demographic and clinical data. National HES data for 1993/4 along with regional data for 1994/5 and 1995/6 would be used to set baseline levels. Regional data would be used to monitor changes in each of these services. Members of the team have considerable expertise in such analysis at both regional and national level and are confident about being able to negotiate national HES through the National Casemix Office, as has been the case for other projects. (One of the team -[name] - works part time for the National Casemix Office.) Local HES data would be obtained via the TPP site/DHA. Preliminary consultations with Scottish Home and Health Department statisticians indicates that Scottish routine data are highly compatible with English HES and of higher quality. There should be no great difficulty producing an Anglo-Scottish analysis of activity trends. Routine data would have to be supplemented by collection of data at TPP level on use of non-NHS services. This could be obtained from TPP practice software for those sites reporting use of non-NHS services during the fieldwork described in the previous main section.

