The work will be undertaken on a consultancy basis by the researchers employed already by members of the evaluation consortium in Edinburgh, Manchester, York, Bristol, Southampton and London to undertake the 'core' evaluation.

It is unlikely that more than 20 TPP sites will intend to contract for A&E separately from their parent health authority. For each of these sites, information will be collected from the main provider of A&E care. It is assumed it will take two days to collect information from each provider and half a day to write-up the findings. Co-ordinators at the London School of Hygiene and Tropical Medicine (JD and CS) will organise the study, provide support and collate the overall results.

MAIN STUDY OF A&E ATTENDANCES FROM DATA ROUTINELY COLLECTED IN A&E DEPARTMENTS

Methods

Selection of TPPs and A&E Depts

Data on A&E attendances will be collected in A&E departments selected after the feasibility study and serving TPP sites which have a clear intention to purchase A&E and emergency care separately from the health authority. As far as possible, departments will be selected so as to cover combinations of the following factors:

block and variable cost contracts; large and small TPPs; metropolitan, suburban or rural sites.

Where there is more than one TPP in a 'cell' (a cell being, for example, large TPP + block contract + suburban) the choice will be based on the quality of the local information systems. If there are many empty cells it may be necessary to restrict the number of explanatory factors considered.

The number of A&E departments providing services to each TPP as well as the availability of minor injuries facilities will have to be considered. In general, TPPs will be chosen in which one A&E department is used by more than 70% of A&E attenders, in which case only that A&E department will be studied. Subjects (patients of GPs in TPP practices) and controls (patients of GPs outside such schemes) will be selected from the same departments. For the 'minority' providers, a broad indication of changes in attendance rates will be given by HES data on emergency admissions from the component of the evaluation on activity changes (see section 5.1, above).

Information to be collected

The main information needed should be recorded routinely by A&E departments for each attendance. The most important items will be:

GP (registered or referring)
date of birth
sex
broad disease category/condition

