method of referral (eg self or GP; local definitions to be clarified)
method of transport to A&E
time first arrived in A&E
time first seen
time of exit
disposal (eg admission or home)
letter to the GP

Other less crucial but nonetheless desirable information would include:

ethnicity postcode time of day examined professional examined by diagnostic tests

If the extent to which patients receive accident and emergency care in hospital without attending a casualty department (eg a minor injuries unit) is of concern, a prospective system will be set up, with clinicians recording the basic patient details. It is not possible to be more precise about this until local practices are identified. Where specific alternative sources of care have been set up such as minor injury clinics, activity data for these will also be sought. Changes in the use of A&E services will be interpreted in the light of such services or new approaches to care developed by the TPP practices (obtained from the 'core' project).

Where TPP practices have their own information on the number of A&E attendances by hospital in the pre- and post-TP periods, this will be used to check where patients of TPPs are attending for A&E care, and to validate the data collected from the A&E sites.

Number of sites to be analysed

The number of sites analysed will depend upon the adequacy of data on A&E attendances where, if the routine data are adequate and can be downloaded for analysis, it will be possible to examine detailed time series of attendances. Data will also be collected from as many of the A&E departments which the TPP patients attend for A&E as have adequate computerised data. The introduction of variable-cost A&E contracts may well be preceded, or at least accompanied, by improvements in A&E and GP data systems. For A&E departments with good data, information on all patients will be collected, starting at least four months before the introduction of TP, and continuing for 15 months.

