If few of the routine information systems in A&E are adequate, ad hoc studies will be necessary involving more limited numbers of patients. A researcher will collect data on attendances for patients from TPP and selected reference practices from paper records at each A&E department. At different periods the researcher will collect information on patients attending during the day and out of hours. The number of weeks the researcher will spend in each A&E department will depend on the number of attendances by patients from TPPs and reference practices. The target will be 200 patients per subgroup (ie for each A&E department, before and after the introduction of TP, and for TPP patients and for reference practice patients). This would give 95% confidence intervals of, for example, 19%-

32% on 25%, and 43%-57% on 50%. Aggregating subgroups to 400 would give 95% CIs of 21%-29% and 44%-56%, respectively.

Using information obtained from the Department of Health on the number of new and follow-up attendances at A&E departments in larger hospitals, at least 30,000 attendances would be expected per A&E department per year. Assuming a 40% coverage of the population by the larger TPPs, it would take about a week to accumulate the necessary number. If the coverage is only 10%, it would take about 4 weeks.

Analysis

The experience of TPP and reference practice patients in the pre- and post-TP periods will be compared with respect to:

rates of attendance (overall, by time of day, by age group, by method of transport to hospital, by broad disease category);

length of time waiting (in casualty before being examined, in casualty from entry to exit);

proportion attending for either 'primary care'-type treatment or conditions which were amenable to treatment in primary care;

rates of diagnostic tests performed;

proportion of attenders admitted to hospital;

proportion of self-referred to GP-referred patients (route F compared to route E as shown on figure 7.1);

and, proportion of patients where letter sent to GP, and content of the letter.

The dependent variables will mainly be proportions. Analyses will involve between-group comparisons of proportions with confidence intervals, and if there are sufficient data on potential confounders, logistic regression. Waiting times will be analysed using medians and/or means with standard errors.

MAIN STUDY OF EMERGENCY ADMISSIONS

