Patients may take several alternative pathways to admission, some involving contact with a GP and others not (as shown in figure 7.1). All possible pathways will have been identified in the feasibility study (above) as will the definition of an emergency admission in each study hospital.

The extent to which patients have used routes D,E,F (on figure 7.1) will largely have been measured in the study of attendances in A&E. However, not all patients who are admitted as an emergency will have attended A&E - some are admitted directly to a hospital ward from home or from outpatients (routes A, B, C). The numbers of patients using these routes may increase as a result of total purchasing, especially for patients with chronic disease who are well known to the hospital. This part of the study will identify the total volume of emergency admissions, the proportion which follow routes A-C to admission, and the casemix of patients admitted.

Methods

Selection of TPPs and hospitals

Four study hospitals will be selected from those used in the study of A&E attendances (outlined above).

Source of information

Firstly, all patients from TPPs and reference practices who were admitted as an emergency at the four hospitals will be identified using data from the patient administration system, information from casualty records already carried for the A&E study, and information from ward admission books or nursing 'Kardex'. Secondly, the route by which the patient was admitted will be identified using information from the casualty record or from the casenotes or the patients themselves. Thirdly, the definition (official and working definitions) of emergency admissions in each hospital will be identified during the study periods.

Analysis

The analysis will involve examining:

the rate of emergency admissions in the before- and after-TP periods and in comparison with reference practice patients;

the total volume of emergency admissions for patients from TPPs and reference practices as compared with those recorded on HES data;

the proportions of patients taking different routes into hospital, such as bypassing their GP;

the main diagnosis and age recorded on discharge data;

whether there was any change in the official or working definition of an 'emergency' admission.

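### The A&E study gives two rules on which departments are counted, and HES emergency admissions cannot indicate attendance at the departments left out

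*Protocol*

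**What the plan says.** Unless noted, these statements are in the protocol's component on accident and emergency care and emergency admissions.

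- **Selection of TPPs and A&E Depts.** On the choice of sites: "In general, TPPs will be chosen in which one A&E department is used by more than 70% of A&E attenders". On what is then counted at such a site: "in which case only that A&E department will be studied". On the comparison group: "Subjects (patients of GPs in TPP practices) and controls (patients of GPs outside such schemes) will be selected from the same departments". On the departments not studied: "For the 'minority' providers, a broad indication of changes in attendance rates will be given by HES data on emergency admissions", with a pointer to Section 5.1.
- **Number of sites to be analysed.** "Data will also be collected from as many of the A&E departments which the TPP patients attend for A&E as have adequate computerised data".
- **Information to be collected.** Where TPP practices hold their own counts by hospital for both periods, these serve to check where their patients go and to validate the department data. Activity data are also sought from alternatives such as minor injury clinics. No matching check is stated for reference practices.
- **Analysis.** The first comparison listed is "rates of attendance (overall, by time of day, by age group, by method of transport to hospital, by broad disease category". The proportion of attenders admitted is another listed outcome.
- **Main study of emergency admissions.** "not all patients who are admitted as an emergency will have attended A&E". The text adds that the direct routes may be used more under TP.
- **Section 5.1, Method.** "HES can provide up-to-date data on all inpatient and day case episodes".

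**The concern.** The A&E introduction hypothesises that TP will reduce attendance, including attendance for conditions that primary care could treat. A count confined to one department measures two things at once: how often patients attend, and where they go. Something must separate the two.

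The protocol is unclear on this in two ways. It states two different rules for which departments supply data. And where it relies on the narrower rule, the tool it offers for the remainder is a count of hospital admissions, which is a different event from an attendance. If TPP patients change department and reference patients do not, the study could report a change in attendance that did not happen, and the HES series could not correct it.

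**Working it through.** The plan gives no figure for this point, so there is nothing to reproduce. The check sets the passages against each other and then sizes the effect.

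**1. Which departments count.** Under the selection text, a site that meets the 70% criterion has one studied department. Under the text on number of sites, the same site has as many departments as have adequate computer records. For a site whose second department has good records, the first rule excludes that department and the second includes it.

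**2. Whether HES admissions track attendance.** At a department outside the study, write

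H = a × A + B,

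where H is emergency admissions in HES, A is attendances, a is the fraction of attenders admitted, and B is emergency admissions that bypass A&E. H follows A only if a and B stay fixed. The protocol lists a as a study outcome and says the routes in B may grow with TP.

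- *Attenders sent home.* HES shows at most the fraction a of any attendances that move. The documents give no value. If a is 10% to 25% (assumed), HES misses 1 − a = 75% to 90%. If only minor cases move, it shows none.
- *Direction.* Suppose A falls by 50 with a = 20% (both assumed). That removes 0.20 × 50 = 10 admissions. If B rises by more than 10, HES goes up while attendance goes down.

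**3. Size of a misread shift.** Let s be the main department's share of TPP attendances and x the share of all TPP attendances that moves elsewhere, with the total unchanged. The rate at the main department changes by −x/s.

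| s | x = 2 points | x = 5 points | x = 10 points |
|---|---|---|---|
| 70% | −2.9% | −7.1% | −14.3% |
| 90% | −2.2% | −5.6% | −11.1% |

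Per 1,000 attendances with s = 70% and x = 5 points, the main department goes from 700 to 650 (−50/700 = −7.1%) and the others from 300 to 350, so the total stays at 1,000. At a = 10% to 25%, HES would register 5 to 12.5 of the 50 that moved. Counting every department gives a change of 0%. The 70% row is the floor of the selection rule, and every x is an assumption. If x is negative (movement towards the main department), the sign reverses.

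**4. What the controls remove.** The apparent difference between groups is approximately −x_T/s_T + x_R/s_R, with T for TPP and R for reference patients. A local change that moves both groups by the same proportion cancels. A shift confined to TPP patients does not. Nor does an equal shift when the shares differ: with x = 5 points in both groups, s_T = 70% and s_R = 90% (assumed), −7.1% + 5.6% leaves about −1.6 points before rounding. The 70% criterion is not stated for reference practices.

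**The case against.** The case on the other side is substantial.

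- The protocol does not rely on the main department alone. It also provides for data from other departments with adequate records, TPP practices' counts by hospital, and minor injury clinic activity, and it says changes in A&E use will be interpreted in the light of such services. This stands. A reader might infer that attendance is counted only at the main department and that any diversion will be read as a fall; these provisions do not support that.
- HES is offered only as a broad indication, and the analysis list does not combine it with attendance rates. This stands as to its role. It does not rescue the indicator, which can move the wrong way. Section 5.1 itself says A&E use is studied separately because routine activity data are lacking.
- Section 3 (Choice of reference practices) asks that reference practices in the A&E study use the same providers, and Table 3.2 adds minor injury provision. So the reference group is not unconstrained, although no share is set for it.
- A reader might infer a bias in favour of TP. The documents do not establish it. Annexe 5 raises change of provider under emergency admissions, expects it only at the margin, and ranks it below changes in admission rates and length of stay. Nothing shows that diversion would occur, be confined to TPP patients, or run away from the main department.
- Section 2 describes the A&E study as a feasibility exercise at that stage, and the A&E introduction already names local choice of A&E site as a possible confounder. That makes the text easier to amend; it does not reconcile it.

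What remains is that the safeguards are conditional. They need adequate computer records at the other departments, or practices that hold counts, and the practice-count check covers TPP practices only.

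**Conclusion.** The point holds in a limited form. The two rules on departments conflict and must be reconciled, and HES emergency admissions should not be used to indicate attendance. Where the other departments lack usable data and practices hold no counts by hospital, a change in where TPP patients attend can be misread as a change in whether they attend. With a 70% share and unchanged total use, a 5-point shift away shows as a 7.1% fall and a 10-point shift as 14.3%. At a 90% share the figures are 5.6% and 11.1%. These rest on assumed shifts specific to TPP patients, and movement towards the main department would produce an apparent rise. They show what could go undetected; they do not predict a bias in a known direction.

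**What to change.** - Reconcile the two subsections in favour of the wider rule: data from every attended department that has adequate computer records.
- Delete the sentence that uses HES emergency admissions as an indicator of attendance. HES keeps its place in the study of emergency admissions.
- Seek attendance counts by practice and period for reference practices as well as TPP practices, wherever departments or practices already hold usable records, so that the check on where patients attend is the same in both groups.
- Check the main department's share of attendances for reference practices too.
- Where such counts cannot be had, report the outcome as *attendance at the main department* and draw no conclusion about total attendance.

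This should be settled before pre-intervention data collection, which the A&E schedule starts in January 1996. The cost is wording plus some extra data requests. Those may not always succeed, since the A&E introduction says data quality varies and the scope for downloading is unclear. At some sites the price will be a narrower conclusion.
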